2.1 Outcomes

The primary and secondary outcomes presented below are also summarized in Table 1.

2.1.1 Primary outcome

The primary outcome is symptomatic hyponatraemia, as defined by a primary or secondary diagnosis of hyponatraemia (ICD-10 code: E87.1) recorded in Sweden and Denmark, and by a discharge diagnosis in the German Pharmacoepidemiological Research Database (GePaRD). Thus, diagnoses from within hospital inpatient and specialist outpatient care will be considered in the Swedish and Danish data sources. Primary and secondary diagnoses of hyponatraemia will be considered equally important in the Swedish and Danish data sources. In the German GePaRD, the focus will be on discharge diagnoses, which are inpatient (not outpatient) diagnoses and in this way outcomes will be assessed based on hospital data in Germany.

An incident event is defined as the first record of symptomatic hyponatraemia during each patient's follow-up. The incidence rate of the primary outcome will be modelled using Poisson regression. If recurrent events of symptomatic hyponatremia have been observed, a Cox model for recurrent events may be applied. If the Poisson regression fails to converge, the unadjusted rate will be presented instead as seen in Table 9 in the row with 'Mean unadjusted rate of events (events/1000 person-years)'.

2.1.2 Secondary outcomes

The secondary outcomes for this study are the following events:

1. Hyponatraemia requiring hospital intensive care, defined as a primary or secondary diagnosis of hyponatraemia (ICD-10: E87.1) recorded in an intensive care unit.

This outcome will only be evaluated in Sweden using data collected from the Swedish Intensive Care Registry (SIR), as information to distinguish between hospital inpatient care in general and intensive care in particular is not available in the Danish national registries or the German GePaRD.

Only incident events (first hyponatraemia record from within hospital intensive care during followup) will be considered.

2. Clinically significant hyponatraemia, defined as a serum sodium concentration of <130 mmol/L.

In addition, hyponatraemia by level of severity will be evaluated, where *mild* hyponatraemia is defined as a serum sodium concentration of above 130 to less than 135 mmol/L, *moderate* as a serum sodium concentration of above 125 to less than 130 mmol/L, and *severe* as a serum sodium concentration of less than or equal 125 mmol/L.

The Danish National Laboratory Database Research Table will be used to evaluate the level of severity using actual measurements of plasma sodium levels. The evaluation of this outcome will be restricted to patients residing in the four Danish regions covered by the database.

Incident and recurrent events will be considered and analysed separately.

3. All-cause mortality, defined as death from any cause.

This outcome can be evaluated in all data sources: in Denmark and Sweden using the national cause of death registries, and in Germany will BIPS identify death and date of death using a database-specific algorithm taking into consideration discharge from hospital due to death and end of insurance due to death.

4. Major adverse cardiovascular events (MACE), defined as a record of myocardial infarction or stroke, (see Table 72 for a list of diagnosis codes used to define these conditions) recorded in each relevant country data source. In Sweden and Denmark, fatal events of myocardial infarction or stroke are also considered as MACE (as cause of death is available). MACE is a composite endpoint.

In addition to overall MACE events, MACE requiring hospital intensive care defined as a primary or secondary diagnosis of MACE recorded in a hospital intensive care unit (ICU) will be reported in Sweden.

5. Major venous thromboembolic (VTE) events, defined as a record of a deep vein thrombosis, pulmonary embolism or portal vein thrombosis (see Table 72, for a list of diagnosis codes used to define these conditions) recorded in each relevant country data source. In Sweden

and Denmark, fatal events of VTE are also considered (as cause of death is available). VTE is a composite endpoint.

In addition to overall VTE events, VTE events requiring hospital intensive care defined as a primary or secondary diagnosis of VTE events recorded in a hospital intensive care unit (ICU) will be reported in Sweden.

Fatal and non-fatal MACE and VTE events will be assessed separately in Denmark and Sweden. Fatal events will only be assessed in Denmark and Sweden using the national registries. Information on cause of death is not available in the German GePaRD unless the patient is dying in the hospital, but German data will not be included in the analysis. For fatal events, death from a MACE or VTE event recorded as the underlying or contributory cause will be considered. For non-fatal MACE and VTE events, primary and secondary diagnoses will be considered equally important (in Germany: discharge diagnoses). Incident events of MACE and VTE in the study time period will be analysed.

6. Acute exacerbation of congestive heart failure.

Given that cardiac insufficiency is a contraindication for the use of Nocdurna ®, the incidence of acute exacerbation of congestive heart failure among patients who have chronic cardiac insufficiency is considered an exploratory outcome in this study.

The outcome will only be analysed among patients with prevalent chronic heart failure. Prevalent chronic heart failure will be defined as ever having had a primary or secondary diagnosis of heart failure (ICD-10: I50; in German GePaRD: outpatient or inpatient diagnosis) before the index date, but no recorded primary diagnosis of heart failure from hospital inpatient care or the acute and emergency ward in the 6 months prior to the index date (German GePaRD: discharge diagnoses). Among these patients, acute exacerbation of heart failure will be defined as a primary diagnosis of acute or acute-on chronic heart failure from hospital inpatient care or the acute and emergency ward, or death from heart failure as the underlying or contributory cause, see Figure 2 for a simple description. Non-fatal events of acute exacerbation of heart failure will be evaluated in all three countries, while fatal events will only be evaluated in Denmark and Sweden.

In addition, a subgroup analysis of all patients adhering to the label as assessed by the proxy based on diagnosis and contra-indications (as available) will be conducted.

7. MACE and VTE events resulting in treatment withdrawal of Nocdurna ® in Sweden.

Serious events resulting in treatment withdrawal of Nocdurna ® will be evaluated in the Nocdurna ® exposed group only in Sweden. Treatment cessation of Nocdurna ®, defined by a time after prescription longer than the permissible gap, will be defined as the end of an on-treatment period. Serious events will be evaluated in 14 days prior to the treatment cessation date.

Serious MACE and VTE events will be defined as a primary or secondary diagnosis of MACE or VTE recorded in a hospital intensive care unit. This can only be evaluated in Sweden.

Variable	Definition	Countries in which outcome assessed
Primary outcome		I
Symptomatic hyponatraemia	Primary or secondary diagnosis of hyponatraemia (E87.1)	Denmark, Germany (hospital discharge diagnosis for in-patient hospitalization), Sweden
Secondary outcomes		
Hyponatraemia requiring hospital intensive care	Primary or secondary diagnosis of hyponatraemia (E87.1) from hospital intensive care	Sweden
Clinically significant hyponatraemia including hyponatraemia by severity	Serum sodium concentration <130 mmol/L Mild hyponatraemia: serum sodium concentration 130 to<135 mmol/L Moderate hyponatraemia: serum sodium concentration above 125 to<130 mmol/L Severe hyponatraemia: serum sodium concentration ≤125 mmol/L	Denmark
All-cause mortality	Death from any cause	Denmark, Sweden, Germany
Major cardiovascular events	Primary or secondary diagnosis of cardiovascular death (underlying or contributory cause), myocardial infarction or stroke	Denmark, Germany (non-fatal events only; discharge diagnosis for in-patient hospitalization) Sweden
Major venous thromboembolic events	Primary or secondary diagnosis of deep vein thrombosis, pulmonary embolism, portal vein thrombosis, or death from either of these conditions as the underlying or contributory cause	Denmark Germany (non-fatal events only; discharge diagnosis for in-patient hospitalization) Sweden
Acute exacerbation of congestive heart failure	Primary diagnosis of acute or acute- on-chronic heart failure from hospital inpatient care or the acute and emergency ward, or death from heart failure as the underlying or contributory cause	Denmark Germany (non-fatal events only; discharge diagnosis for in-patient hospitalization) Sweden
Serious adverse events	Primary or secondary diagnosis of MACE or VTE leading to admission to a hospital intensive care unit	Sweden

Table 1. Definitions of primary and secondary outcome variables

3 TRIAL DESIGN

3.1 General Design Considerations

This is a multi-country, cohort study using secondary data collected from research databases and administrative national healthcare registries in selected European countries (Denmark, Germany, and Sweden).

Cohorts of patients using Nocdurna ® or treatment of LUTS (new user) will be identified from existing data sources in each country of study. These data sources hold information on dispensed prescriptions, patient demographics and diagnoses. The LUTS contextual cohort will be comprised of patients based newly starting treatments associated with polyuria, receiving relevant standard care. For secondary comparative analyses, the comparator group for Nocdurna ® patients will be LUTS patients.

The study period will be from the date of launch of Nocdurna ® until the date of latest data availability in each country, considering that the final study report is planned for 2023. Given the lag time of data updates and time allocated for analysis and reporting, last data included in the final report is likely to be up to end of 2021. Historical data, reflecting a minimum of 12 months before initiation of treatment with Nocdurna ® (or initiation of treatment for LUTS), will be used to assess characteristics (e.g., demographics, indication, comorbidities, and co-medication) at the index date.

In addition to the final study report, there will be 2 interims reports (in 2021 and 2022) on study progress and any emerging safety data. The final report will include meta-analysis for combining the safety in the three countries.

3.1.1 Sample Size

The study will be conducted among patients using Nocdurna ® in the outpatient setting in three European countries: Denmark, Germany and Sweden. These countries have been selected following careful consideration of multiple factors: a feasibility assessment of the ability of candidate data sources to address the study objectives, recommendations by the Swedish Medical Products Agency (MPA), and expected uptake of Nocdurna ® in the candidate countries. Sales data was used as an indicator of uptake of Nocdurna ® to ensure a sufficiently large exposed population as shown in Table 2. Based on the information contained in the data sources available in the candidate countries and the estimated extent of exposure to Nocdurna ® based on available sales data in European countries, Denmark, Germany and Sweden were chosen as countries of study.

Country	Share of Nocdurna ® sales in 2018 (%)	Nocdurna ® commercial launch date
Germany	40	January 2017
United Kingdom	22	November 2016
Belgium	9	March 2017
The Netherlands	7	November 2016
Sweden	7	January 2017
Denmark	5	August 2017

Table 2. Nocdurna ® sales statistics (2018) and launch dates in candidate countries of study

The study will use data from countries where the uptake of Nocdurna ® is expected to provide a sufficiently large population of exposed patients. Therefore, the sampling frame has been constructed using the distribution of sales data in the EU.

3.1.2 Sample size for primary outcome analysis

All available patients with a Nocdurna ® prescription in the study period will be included in this study. The primary objective is descriptive.

In addition to the feasibility study detailed above, Nocdurna ® sales data was reviewed to estimate the available number of patients. Table 3 shows the patient estimate based on the share of Nocdurna ® sales in 2018, the number of oral lyophilisates, 50% adherence, and coverage of the database per country of this study. GePaRD coverage is approximately 18% of the German population.

Country	Share of Nocdurna ® sales in 2018 (%)	Number of oral lyophilisates	Patient estimate assuming 50% adherence	Patient estimate from the Database
Germany	40	661.950	3.678	662
Sweden	7	117.250	651	651
Denmark	5	82.260	457	457

Table 3. Patient estimate for 2018 per country

The patient estimate for Sweden is thus in line with the results from the feasibility study. The coverage and availability of data from Denmark is comparable to Sweden, as both data sources rely on national registers.

Extrapolating the patient estimated from Table 3 to a time period 2018-2021 (end of the study time period), and assuming conservatively that sales remain constant during the time period, the number of Nocdurna ® patients in this study will likely be at least:

•	Germany (GePaRD):	2650
•	Sweden:	2610
•	Denmark:	1830

However, the secondary objective 6 with a sub-population with chronic cardiac insufficiency demands for the analysis of a much smaller sample size and with an even smaller number of events. During the analysis and interpretation of the results these facts must be considered. Since the primary objective in the study is descriptive, no formal sample size has been calculated and this also implies that no statistical hypothesis has been formulated. Calculated p-values are also descriptive.

3.1.2.1 LUTS patients

All the above calculations are only referring to the Nocdurna ® treatment. For the LUTS patients the MEDSTAT.DK database has been used to calculate the number of patients. In 2017 there were 82,035 patients using the diagnose code G04C and 45,270 patients using the ATC code G04BD, a sum with a maximum of 127,305 patients, since some patients could have both drugs. Extrapolating to the study period a sum of approximately 300,000 patients in the LUTS group should be expected. In Sweden the patient number should be a factor 1.7 larger and in Germany a factor 2.3 larger than the patient number in Denmark, while taking the country populations in Sweden into account and the population in Germany and the coverage of the GePaRD database.

N/A

3.1.4 Trial Epochs

N/A

3.1.5 Visits [and Visit Windows]

There are no planned visits in this study. The patients will be followed through the registries.

The planned study period ranges from the date of launch of Nocdurna ® (Table 2) to the date of latest data availability in each country. Thus, the planned study periods are as follows:

- Denmark: 29 August 2016 to 31 December 2021
- Germany: 1 January 2017 to 31 December 2021

• Sweden: 20 January 2017 to 31 December 2021

Historical data, reflecting a minimum of 12 months before index date will be used to assess baseline characteristics (e.g., demographics, comorbidities and co-medications). Thus, the total period for which data will be collected is from at least 12 months before the date of launch of Nocdurna ® to the date of latest data availability in each country.

4 **PROTOCOL VIOLATIONS**

There are no exclusion criteria. Patients that are identified as valid cases will be followed until endof-study.

5 ANALYSIS SETS

5.1 Cohort entry

Cohort entry is defined by the index date.

5.1.1 Index date - Nocdurna ® cohort

The index date is defined by their first ever prescription of Nocdurna ® in the study period.

5.1.2 Index date - LUTS cohort

The index date is defined by their first ever prescription of medication used to treat urinary frequency and incontinence (Anatomic Therapeutic Chemical (ATC) codes G04BD) or benign prostatic hypertrophy (ATC codes G04C) in the study time period.

5.1.3 Cohort exit

Right censoring events – Nocdurna ® cohort

Patients will be followed from the index date to the date of a censoring event: a dispensed prescription for a vasopressin agonist or desmopressin drug other than Nocdurna ®, transfer out of the database, emigration, death or end of the study period, whichever occurs first and irrespective of treatment status (on/off drug). As appropriate, patient will also be followed from index date to the date of the diagnosis of the outcome of interest, or end of treatment of Nocdurna ®.

Right censoring events – LUTS cohort

Patients will be followed from the index date to the date of the censoring event: a dispensed prescription for a vasopressin agonist or desmopressin drug, transfer out of the database, emigration, death or end of the study period, whichever occurs first. As appropriate, patient will also be followed from index date to the date of the diagnosis of the outcome of interest, or the end of treatment of drugs defining the LUTS cohort.

5.1.4 Eligibility criteria

Inclusion criteria – Nocdurna ® cohort

The cohort of Nocdurna ® patients will consist of individuals meeting the following inclusion criteria:

• A first-ever dispensed prescription for Nocdurna ® [desmopressin; Anatomical Therapeutic Chemical (ATC) code: H01BA02; brand name: Nocdurna ®; dose: 25 or 50 micrograms] recorded in the relevant country-specific data source between its launch date and the latest date of data availability in each country. The first-ever dispensation is in the German database, the first dispensation covered by their insurance databases, since patients could

move between different database providers and the first detected dispensation might not be the first-ever.

Note: To identify Nocdurna ® dispensations, first all desmopressin dispensations with the ATC code H01BA02 will be extracted, then the cohort for analysis will be selected using the brand name Nocdurna ® and the dose of Nocdurna ® (25 or 50 microgram).

- Aged 18 years and above on the index date.
- At least 12 months' registration in the relevant country-specific database(s) prior to the index date, to ensure a sufficiently long period of baseline data availability.

5.1.5 Exclusion criteria – Nocdurna ® cohort

The following exclusion criteria will be applied to the Nocdurna ® cohort:

- Treatment with vasopressin or any of its analogues (defined as a dispensed prescription within 6 months (180 days) before the index date [index date -1 day]; ATC codes H01BA), irrespective of formulation or dose/strength.
- Multiple desmopressin drugs dispensed on the index date.
- Patients with missing information on the variables required for the (key) analyses (i.e. missing information on age and sex) will be excluded.

5.1.6 Inclusion criteria – LUTS cohort

Patients meeting the following criteria will be included in the LUTS cohort:

- A first-ever dispensed prescription for a medication used to treat urinary frequency and incontinence (ATC codes G04BD) or benign prostatic hypertrophy (ATC codes G04C) between the launch date of Nocdurna ® and the latest date of data availability in each country. The first-ever dispensation is in the German database, the first dispensation covered by their insurance databases, since patients could move between different database providers and the first detected dispensation might not be the first-ever.
- Aged 18 years and above at index date.
- At least 12 months' registration in the relevant country-specific database(s) prior to the index date, to ensure a sufficiently long period of baseline data availability.

[figure not shown]
The ATC codes used to define the LUTS cohort are summarized in Table 70.

5.1.7 Exclusion criteria – LUTS cohort

The following exclusion criterion will be applied to the LUTS cohort:

- Treatment with vasopressin or any of its analogues (defined as a dispensed prescription within 6 months (180 days) before the index date [index date -1 day]; ATC codes H01BA), irrespective of formulation or dose/strength.
- If a patient according to the above is qualified for both the Nocdurna ® and the LUTS group, this patient's information must be deleted from the LUTS group, since it is expected that the Nocdurna ® group will be the smallest.
- If a prescription for a LUTS drug is found before the study time period, this patient must be excluded, since the later prescriptions will not be the first ever prescription with in study time period.
- Patients with missing information on the variables required for the (key) analyses (i.e. missing information on age and sex) will be excluded.

Figure 1. Inclusion, exclusion and study period start for LUTS treatment as defined above.

This is a safety study (PASS) and all findings are safety related.

6 TRIAL POPULATION

Patients that are identified according to section 5 will be used as the trial population.

6.1 Demographics and Other Baseline Characteristics

6.1.1 Demographics

Descriptive statistics of baseline demographics variables will be tabulated. The categorical variables will be presented at index date and these are gender, ICD 10 code recorded before or at index date, ATC recorded before or at index date. All available time before index date and at least 12 months are used in the calculation of the ICD 10 and ATC codes. The continuous variables are age at index date, length of exposure, number of hospitalisations before index date, number of emergency room visits before index date. Observe that length of exposure is not a baseline demographic variable, but will be described with the same statistical measures.

6.1.2 Vital Signs at Baseline

N/A.

6.1.3 Physical Examination at Baseline

N/A.

6.1.4 Laboratory Effectiveness/Pharmacodynamical Parameters at Baseline

N/A.

6.1.5 Trial-specific Baseline Variables or History of Disease

N/A.

6.2 Medical History

Medical history will be calculated from the ICD 10 codes recorded in the registries used in the three countries. No MedDRA coding will be done.

7 SUBJECT DISPOSITION

The number of potential patients not included in the study will be summarized. The conditions for not including the patients are; age below 18 years at index date, treatment with vasopressin or any of its analogues defined as a dispensed prescription within 6 months (180 days) and for Nocdurna ® patients and multiple desmopressin drugs dispensed on the index date. It is also important that the LUTS patients is having their first dispensation of a LUTS drug after the launch of Nocdurna ® treatment in the investigated country, so that patients using LUTS before the study start date are excluded. The population with the excluded and included patients will be shown in Table 8.

8 PRIOR AND CONCOMITANT MEDICATION

Prior medication will be tabulated from the specifications in the applications to the ethical boards. Only a limited and targeted number of medications have been specified, since asking for all medication would not be needed for answering the medical objectives in the study and getting information about medication outside the medical scope would be a violation of the privacy rules. Previous medication will be tabulated like shown in Table 10.

9 EXPOSURE AND TREATMENT COMPLIANCE

9.1.1 Extent of Exposure

Exposure person-time will be defined for Nocdurna ® patients from the date of first Nocdurna ® prescription. For comparative analyses, equivalent person-time in the LUTS contextual cohort group will be defined from the index date.

Person-time observed from index date to the date of outcome or censoring event will be determined for both the Nocdurna ® group and the LUTS group.

Estimation of exposure periods: Duration of exposure to the respective study drug (Nocdurna \mathbb{R} or LUTS treatment) will be defined based on the estimated supply of drug dispensations. To estimate the supply, the total drug amount of a dispensation is converted into defined daily doses (DDDs; sex-specific DDD for Nocdurna: 25 µg for females, 50 µg for males). The days supplied added to the dispensation date will approximate the end date of a dispensation.

Overlapping dispensations: If a new dispensation of the respective study drug occurs prior to the end date of the previous dispensation, the estimated end date of the latest dispensation will be postponed by the days of overlap.

Permissible gap: If there is a gap after the estimated end date of a dispensation (i.e. there is no new dispensation of the respective study drug covering the first day after the end date of the latest dispensation), the exposure period will be extended. A period equal to the days supplied by the latest dispensation (DDD*1) will be added to the end date of the latest dispensation. In other words, the exposure period continues if a subsequent dispensation occurs within the timeframe of the permissible gap.

End of exposure period: If no subsequent dispensation occurs within the timeframe of a permissible gap, the end of the exposure period will be the last day of the permissible gap.

The above-mentioned considerations apply to both Nocdurna ® and drugs for the treatment of LUTS. For both the Nocdurna ® and LUTS groups, exposure periods start at cohort entry.

There are multiple preparations (multiple ATC codes) defining the treatment of LUTS. All those preparations are considered when defining exposure to LUTS treatment, i.e. concomitant use and switching between different preparations to treat LUTS are allowed within a patient's exposure period. In the Nocdurna ® group, however, only Nocdurna ® dispensations are considered to define exposure periods.

Desmopressin One oral lyophilisate per day Statistical Analysis Plan	Trial Code: 000248	18 August 2021 E-Statistical Analysis Plan-25098 (1.0) Page 25 of 91
90-day supply 2nd nocdurna* dispensation 90-day supply 30-day supply 30-day overlap	90-day permissible gap 3rd nocdurna* disp 90-day sup	
	γ Continuous Nocdurna* Exposure	

*Exposure to drugs for the treatment of LUTS will be estimated analogously.

If a person in the Nocdurna group is prescribed desmopressin in a higher dose than in the Nocdurna defining dose (25 or 50 micrograms) the person-time must be stopped when this higher dose is prescribed. Observe that these drug will have the same ATC code as Nocdurna (H01BA02), but another brand name and a higher dose. In Germany the brand will be used to identify Nocdurna.

Treatment restarts following treatment holiday (larger than the permissible gap) will not be evaluated in this study

Observe that if a patient is using the last of the prescribed/dispensed drugs, the end of treatment will be the last day according to the standard dose as defined in section 5.1.4.

On treatment person-time (exposure time) will be tabulated as shown in Table 10 and graphs will be made as shown in Figure 11, Figure 12, Figure 13, and Figure 14.

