13 CHANGES FROM THE PROTOCOL

The statistical analysis are described in further details and explanatory figures have been added, compared with the outlines in the protocol.

The protocol states that 'Fatal and non-fatal MACE and VTE events will be assessed separately', but this is only possible in Denmark and Sweden. The SAP is updated.

The protocol stated that 'The length of the permissible gap will be varied (shortened or lengthened).', while the SAP specified 'The length of the permissible gap will be shortened'. Also the following has been added '. If two treatments with different ATC-codes are dispensed (or prescribed) on the same day only the treatment with the highest number of supplied days should be kept in the analysis.', since the previous formulation would give too long treatment periods.

Protocol stated in section 9.3.21 that 'If, recurrent events have been observed, a Cox model for recurrent events may be applied which will be detailed in the SAP.' The SAP specifies that this analysis will be presented if more than 5% of the patients has recurrent events.

Meta-analysis is in the protocol 'specified as random effect model', but the analysis has been expanded to both random and fixed effect model in the SAP and this is also reflected in the table shells.

Protocol stated that 'All adverse events/reactions collected for the study will be recorded and summarized in the interim *safety* analysis and in the final study report.' The SAP specifies that 'All adverse events/reactions collected for the study will be recorded and summarized in the interim analysis and in the final study report'. The word 'safety' was deleted since all statistical analysis will be presented in the yearly reports, except the meta-analysis.

The analysis of contraindications have been simplified and corrected compared with the protocol. Only one subpopulation for defining contraindications will be created, not the suggested 3 subpopulation, so that the extra medical conditions in secondary objective 5a, 5b, and 6 have been omitted, since it is not reasonable to have different contraindication at baseline for a possible future event. The usage of concomitant medical usage has also been omitted, since it is the condition at baseline that must determinate initiation of Nocdurna ® usage, not a future concomitant medical prescription, unknown to the prescribing physician at the index date.

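### Overlap carry-over in SAP 9.1.1 is not limited to one LUTS substance, so staggered concurrent LUTS drugs are laid end to end and LUTS on-treatment time is overstated for those patients

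*Protocol*

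**What the plan says.** SAP 9.1.1 builds exposure from dispensed supply. The unit is the study drug, meaning NOCDURNA on one side and LUTS treatment on the other: duration for NOCDURNA "or LUTS treatment) will be defined based on the estimated supply of drug dispensations". Three rules then apply to that unit.

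- Overlap: if a new dispensation comes before the previous one ends, "the estimated end date of the latest dispensation will be postponed by the days of overlap".
- Gap: "A period equal to the days supplied by the latest dispensation (DDD*1) will be added to the end date of the latest dispensation".
- Scope: "The above-mentioned considerations apply to both Nocdurna ® and drugs for the treatment of LUTS".

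For LUTS, every defining preparation counts, and "concomitant use and switching between different preparations to treat LUTS are allowed within a patient's exposure period". For the other cohort, "only Nocdurna ® dispensations are considered to define exposure periods".

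SAP 13 reports an added rule for different ATC codes dispensed on the same day: "only the treatment with the highest number of supplied days should be kept in the analysis". The reason given is that treatment periods would otherwise come out too long. SAP 9.1.1 does not contain this rule, and it says nothing about different LUTS drugs dispensed on different days.

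Protocol 9.3.1 has the same kind of overlap rule and does not restrict it to a single substance either.

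**The concern.** Carrying overlapping days forward is sensible when a patient refills one drug early, because the remaining units will be taken later. It does not fit two different drugs taken on the same days: each day uses up one day of both supplies, so the number of covered days does not grow. Because the rule operates on LUTS treatment as a whole, two LUTS drugs in parallel use are counted as if one followed the other. SAP 3.1.2.1 expects some patients to have drugs from both LUTS classes.

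At stake is the comparability of on-treatment time between the cohorts. NOCDURNA is one product, so this mechanism cannot arise there. The stacked days fall at the end of the LUTS exposure period, after the drugs have run out. They enter the exposure-time summaries and, wherever person-time stops at end of treatment, the later-month LUTS denominator together with any events in those days.

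Neither planned sensitivity analysis in SAP 10.1.3 would reveal this. The zero-gap analysis still shifts the second prescription to the end of the first, and the prescribed-dose analysis alters NOCDURNA patients only.

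**Working it through.** **The plan's own example.** The figure labels in SAP 9.1.1 give two 90-day supplies, a 30-day overlap and a 90-day permissible gap. With dispensations on days 0 and 60, supply ends on day 60 + 90 + 30 = 180 and the gap runs to 180 + 90 = 270. This reproduces the rule for one product.

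**Same rule, two LUTS drugs, one pack each (90 days, assumed).**
- Same day, with the SAP 13 rule: one pack is kept, so supply ends on day 90.
- One day apart: 1 + 90 + 89 = day 180. The days actually covered end on day 91.

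A one-day difference in dispensing date therefore doubles the counted supply.

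**One year of parallel use.** Assumed inputs: drug A on days 0, 90, 180, 270; drug B on days 10, 100, 190, 280; 90 days per pack; gap equal to the last supply (90 days, from SAP 9.1.1).

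1. *Cumulative overlap* (measured against the running, already postponed end date). End = dispensation day + 90 + (running end − dispensation day) = running end + 90. The eight packs give 90, 180, 270, 360, 450, 540, 630, 720. Adding the gap: 720 + 90 = 810.
2. *Non-cumulative overlap* (measured against the previous pack's unshifted end). Last pack on day 280, previous pack unshifted end 270 + 90 = 360, overlap 80. End = 280 + 90 + 80 = 450. Adding the gap: 540.
3. *Union of covered days* (carry-over within each drug only). A ends on day 360, B on day 370. The later is 370; adding the gap: 460.

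| Method | Supply ends | With gap | Ratio to union |
|---|---|---|---|
| Pooled, cumulative | 720 | 810 | 810/460 = 1.76 |
| Pooled, non-cumulative | 450 | 540 | 540/460 = 1.17 |
| Union | 370 | 460 | 1 |

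The text of 9.1.1 does not say which of the first two readings is meant.

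NOCDURNA with four 90-day packs gives 360 (450 with the gap) under the pooled rule and under the union.

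**First and later months.** SAP 10.1.2 caps first-month exposure at 30 days and subtracts 30 days for the later period. Extending the end of supply leaves the first 30 days unchanged as long as the first pack plus its gap already covers them. All the extra days fall in the later period: 780 or 510 days against 430 for this patient.

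**Cohort level, illustration only.** Let a share *s* of LUTS patients follow the pattern above and the rest use one drug (four packs, 450 days). The ratio of mean exposure is [(1 − s)·450 + s·X] / [(1 − s)·450 + s·460], with X = 810 or 540.
- s = 0.10: 486/451 = 1.08, or 459/451 = 1.02.
- s = 0.30: 558/453 = 1.23, or 477/453 = 1.05.

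The documents give no value for *s*. These ratios assume that every dual user is staggered for a full year and that nothing else ends follow-up earlier.

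**The case against.** The strongest reply is that supply-based time may not enter the models at all. SAP 10.1.2 defines time at risk from index date to the first censoring event. SAP 5.1.3 makes end of treatment a stopping point only where appropriate. Table 67 in SAP 16.1 describes the exposure variable behind the Poisson offset as running to the end of the study. Under that reading the rates are untouched. Other text points the opposite way: SAP 10.1.3 expects a shorter gap to reduce both events and exposure time, and SAP 10.2.8 ends exposure time at a switch between cohorts. The documents do not settle this, so a reader who infers that every LUTS rate and rate ratio is distorted goes too far. The effect on the exposure description is clear; the effect on rates is conditional.

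Other parts of the reply also stand.

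- Same-day dispensing of different drugs is already handled in SAP 13. That section lists changes from the protocol, and its difference from 9.1.1 is not in itself an error. What matters is that the rule stops at day 0.
- First-month rates, where the protocol expects the highest hyponatraemia incidence, are essentially unaffected.
- One might argue that a switch adds leftover tablets that were thrown away. The documents say nothing about discarded packs, and SAP 9.1.2 assumes that everything dispensed is taken. The point rests on concurrent use only.
- It would be wrong to infer that NOCDURNA exposure is accurate. Protocol 9.9.2 accepts that it may be overestimated. Only this mechanism is absent there.

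**Conclusion.** The defect holds for different LUTS substances dispensed on different days while supplies overlap. Followed as written, SAP 9.1.1 overstates on-treatment time for these patients, in one cohort only. It affects Table 10, Figures 11-14, and any rate or rate ratio after the first month whose person-time stops at end of treatment. Follow-up that continues regardless of treatment is unaffected.

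For the constructed patient, exposure is 76% too long under cumulative overlap and 17% under non-cumulative overlap. These figures rest on assumed 90-day packs, a 10-day offset and one year of parallel use. The cohort effect of about 2% to 23% is a range over assumed shares of 10% to 30% and both readings of the rule. It is not an estimate for this study, and other censoring would reduce it.

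A longer LUTS denominator might suggest a LUTS rate that is too low and a rate ratio that is too high. The documents do not support that inference: the added days also bring in any events that occur in them, and the event rate in that untreated time is unknown. The direction of bias is not established.

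**What to change.** Amend SAP 9.1.1 as follows.

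- Carry overlapping days forward only between dispensations of the same ATC substance.
- Across different LUTS substances, take the union of the covered intervals, so that supply ends at the latest end date among them. Then add the permissible gap.
- State that overlap within a substance is measured against the running (already postponed) end date, so that all three countries program it identically.
- Let this replace the same-day rule of SAP 13. The union gives the same answer there in the example above (four packs each on the same days: day 360, or 450 with the gap).

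It would help to state in the same amendment which rates stop person-time at end of treatment, since that decides how far the change reaches.

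The cost is one SAP paragraph, a by-substance step in each country's exposure program, and a rerun of the affected LUTS outputs. No new data are needed, and the plan's single-product example (days 180 and 270) does not change.
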